## 1. Background and Significance

Patient compliance with laboratory testing is one of the most underrecognized challenges in developing a treatment plan for acute and chronically ill patients. The ability to offer alternatives to standard venipuncture blood draws would greatly increase a laboratory's ability to provide testing to patients and health care providers.

Currently the venipuncture in the antecubital fossa area is the standard procedure for blood collection. Unfortunately, this can be painful and the veins in this area could be hard to access in some patients (including kids).

The fingerstick blood draw has been used as an alternative for calcium and glucose measurements. Capillary blood is used in neonatal population as well.

The procedure of finger-prick blood collection may in some instances cause minor levels of stress and anxiety to individuals as well as acute levels of pain at the time of "prick." We are attempting to reduce stress and anxiety with this new device that aims to avoid the pain of this procedure.

Aiming a less painful, potentially easier alternative we devised a novel that can be applied distally on the digit prior to the blood collection procedure and may provide analgesia through propylene glycol, a liquid coolant that is run through tubes in the device to safely cool tissue to 0°C to 7.5°C to achieve numbing. We hypothesize that this device will safely and effectively reduce the pain associated with the fingertip pricks and increase the amount of capillary blood collected. Besides, we believe in the future this novel could be used for other finger or procedures of the nail unit.

Multiple punctures with a large lancet were a frequent cause of discomfort among patients and should be given consideration since the desire to avoid a painful venipuncture is a common reason given as justification to consider this type of sample. With this new device the discomfort will be reduced by its application followed by the numbness of the finger.

Therefore, capillary sampling should be considered on patients who refuse venipuncture or venous access cannot be established. This method is also considered to be useful for screening of blood disorders.

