## **2. Specific Aims and Objectives**

To evaluate a novel tissue-cooling device for pain management during needle sticks and /or blood draw on the fingertips.

The study will use a device developed in conjunction with Sunrise Labs, an experienced medical device development firm (<https://www.sunriselabs.com/>).

The specific aims of the study are as follows:

Aim 1. Evaluate the pain management capability of the tissue-cooling device for finger prick blood draws compared to standard of care (antecubital venipuncture).

Aim 2. Quantify the amount of blood collected by the finger pricks.

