#### *Visit 1*

Visit 1 is expected to last approximately 1 hour.

The following assessments will be performed during Visit 1:

- Review of eligibility criteria
  - Ring size measurement
- Review of medical history and medications
  - Urine pregnancy test (for female participants of childbearing potential)
- Take blood pressure (2 times before treatment; 2 times after) using a standard hospital owned blood pressure arm cuff device.
- The novel digit cooling device will be turned on and allowed to chill to -3 degrees Celsius prior to the procedure.
- Two fingers (one on each hand) will be pricked during Visit 1: the “control” digit and the “chiller” digit.
  - The first finger to be pricked will be randomized.
  - The pricked fingers will be either the fifth or third digit(s).

- Pricks will be administered using a sterile and disposable McKesson Push-Button 17G or 23G Safety Lancet, bought specifically for this trial.
- Subjects will be instructed on how to report a pain score for each prick. A visual 10-point pain scale will be used (see below).
- The procedure for the “control” digit is as follows:
  - A Beurer oximeter will be used to measure the percent oxygen and pulse rate.
  - A thermal camera will be used to measure the temperature of the finger tip.
  - One prick will be applied to the ventral tip of the “control” digit. A pain score will be reported by the subject.
  - The pricked finger will subsequently be held over a single-use Whatman 903 filter paper. Approximately every ten seconds after the prick, the filter paper will be gently applied to the blood drop to absorb the blood. This will be repeated on new locations of the filter paper until blood flow stops. At least one Whatman 903 filter paper will be used per finger prick. The Whatman 903 filter paper will be imaged.
- The procedure for the “chiller” digit is as follows:
  - A sterile glove will be placed on the “chiller” hand. The top of the fifth or third finger of the glove will be cut and rolled down to the base of the finger to promote venostasis and blood harvesting.
  - A Beurer oximeter will be used to ensure there is not enough blood flow to measure the percent oxygen and pulse rate in the finger.
  - A thermal camera will be used to measure the temperature of the finger tip.
  - A layer of glycerol will be applied circumferentially to the intended treatment area on the “chiller” digit.

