  - No more than one minute after sterile glove application, the novel digit cooling device will be applied to the “chiller” digit on the area with glycerol.
  - No more than four minutes after the novel digit cooling device is applied to the “chiller” finger, one prick will be applied to the ventral tip of the “chiller” digit. A pain score will be reported by the subject.
  - The pricked finger will subsequently be held over a single-use Whatman 903 filter paper. Approximately every ten seconds after the prick, the filter paper will be gently applied to the blood drop to absorb the blood. This will be repeated on new locations of the filter paper until blood flow stops. At least one Whatman 903 filter paper will be used per finger prick. The Whatman 903 filter paper will be imaged.
- Post-procedure images will be taken of the tips of the “control” and “chiller” digits.
- A thermal camera will be used to video record the fingers starting with the sterile glove application on the “chiller” finger until the post-procedure images have been collected by an encrypted iPhone 12 Pro.
- Regular video recording with an encrypted iPhone 12 Pro will be done simultaneously.

Wong-baker pain assessment on a visual analog pain scale:

©1983 Wong-Baker FACES Foundation. [www.WongBakerFACES.org](http://www.WongBakerFACES.org)  
Used with permission. Originally published in *Whaley & Wong's Nursing Care of Infants and Children*. ©Elsevier Inc.

- The device will be removed from the digit
- Study staff will document any anticipated side effects or Adverse Events that occur during the study visit.
- A licensed physician investigator will be operating the study device during the procedure.

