#### **Devices to be used**

#### **Experimental Cooling Device description**

The experimental device is a cooling device intended to provide analgesia during needle sticks for blood draws on digits extremities. The device is a circulating fluid chiller using a propylene glycol / water mixture (4:7) flowing through an applicator designed to cool the conductive nerves in the digit to a temperature below which nerve conduction from the distal portion of the digit reduces and/or ceases. The device is designed with two u-shaped coolant tubes that are applied to the circumference of tissue at the base of a digit. The coolant tubes appose each other to surround the digit and then are brought together with a screw /spring mechanism to apply sufficient pressure to the main arteries feeding the digit to partially occlude blood flow, thereby enhancing the tissue-cooling effect.

The clinician monitors tissue blanching while applying the applicator to ensure there is sufficient but not excessive occlusion.

With a circulating coolant temperature of -3°C, the device will cool tissue in contact with and near proximity to the cooling tubes to 0°C to 7.5°C. The subject's hand will be wearing an sterile glove to provide a barrier between the cooling ring and skin. The fifth finger of the glove will be removed sufficiently to expose the area to be pricked in this study. This circumferential ring of cold and partially occlusive pressure on the digit will provide analgesia by blocking nerve conduction signals from leaving the digit and signaling pain to the central nervous system. The pressure on the arterial vessels assists tissue cooling by reducing blood flow and therefore the amount of heat transferred to the cooled tissue.

This device poses no risk to the subject if left on for 10 minutes or less. The device will only be on the subject for 7 minutes, and glycerol will also be used to further decrease any risk to the subject.

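### The rolled glove and glycerol go on the chiller digit only, so a blood difference belongs to the package, not the device; the chilled hand and the matching of digit and lancet gauge have no stated rule

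*Combined protocol and SAP*

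**What the plan says.** **Chiller digit (Section 6.a, Visit 1).** A glove goes on the chiller hand. The tip of the relevant glove finger is cut and the rest is "rolled down to the base of the finger to promote venostasis and blood harvesting". The next item is a flow check: "A Beurer oximeter will be used to ensure there is not enough blood flow" for a reading. A thermal reading and glycerol follow, and then the device: "No more than one minute after sterile glove application, the novel digit cooling device will be applied".

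**Control digit (same section).** Oximeter reading, thermal reading, prick, pain score and blood collection. No glove, glycerol or clamp is listed.

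**What is credited to the device.** Section 1 hypothesises that the device will reduce pain and "increase the amount of capillary blood collected". In Section 2, Aim 2 is neutral: "Quantify the amount of blood collected by the finger pricks". Aim 1 names antecubital venipuncture as the comparator. The device description under Devices to be used says: "This circumferential ring of cold and partially occlusive pressure on the digit will provide analgesia". It mentions the glove as a barrier between ring and skin.

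**Allocation and matching (Section 6.a, Visit 1).** "Two fingers (one on each hand) will be pricked during Visit 1". "The first finger to be pricked will be randomized". The digit may be the fifth or the third, and the lancet 17G or 23G. Section 4.a and the device description refer to the fifth finger only.

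**The concern.** There are two separate problems.

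*Attribution.* A step whose declared purpose is to help blood harvesting is applied to one digit only, and the amount of blood is one of the outcomes. If the chiller digit yields more blood, the glove is a competing explanation that the protocol itself supplies. Crediting the device alone would be an over-claim.

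*Assignment.* Each subject is their own control across two hands, so the contrast is fair only if nothing but the condition differs systematically between the hands. On the plain reading, the randomisation sentence sets which condition goes first and says nothing about which hand is chilled. Digit and lancet gauge may also differ between the two pricks, and gauge is part of the painful stimulus. Choices made in a consistent direction would bias the contrast. Haphazard choices would only add noise.

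**Working it through.** **1. Attribution: a comparison of steps**

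| Step (Section 6.a, Visit 1) | Control digit | Chiller digit |
|---|---|---|
| Rolled glove | not listed | yes |
| Oximeter | measures saturation and pulse | confirms flow too low to read |
| Glycerol | not listed | yes |
| Clamp and cooling | not listed | yes |
| Prick, pain score, filter paper | yes | yes |

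The low-flow check is listed after the glove and before the device, so as written the glove step is expected to restrict flow by itself. Glove and device are both present on every chiller digit and both absent from every control digit (12 of 12 subjects, or 16 of 16). The two indicators are identical, so their separate effects are not estimable whatever the sample size.

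**2. The plan's own figure**

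Section 9 gives n = 16 for power 0.95, two-sided 0.05, SD 2, but states no effect size, so 16 cannot be reproduced from its inputs alone. Solving backwards, a paired t-test with SD of the difference 2 implies a difference of 1.93 points. An independent t-test with 16 per arm and SD 2 per score implies 2.64 points. Both fit, so the figure does not settle which SD is meant, and each reading is carried below.

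**3. Size of a systematic choice of hand, digit or gauge**

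The documents give no effect size for these, so shifts *b* of 0.5 and 1 point are assumptions. With no package effect, the chance of p<0.05 is the power of a two-sided 0.05 t-test on the signed difference, from the noncentral t distribution:

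- Paired, SD of difference 2: noncentrality = b√n / 2, n − 1 degrees of freedom.
- Paired, SD 2 per finger and no correlation: SD of difference = 2√2 = 2.83; noncentrality = b√n / 2.83, n − 1 degrees of freedom.
- Independent t-test as named in Section 9, SD 2 per finger, uncorrelated fingers: noncentrality = b / (2√(2/n)), 2n − 2 degrees of freedom.

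Example: b = 1, n = 12, first version: 1 × √12 / 2 = 1.73 on 11 degrees of freedom gives 0.353.

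| Test and SD reading | n=12, b=0.5 | n=12, b=1 | n=16, b=0.5 | n=16, b=1 |
|---|---|---|---|---|
| Paired, SD of difference 2 | 0.1245 | 0.3528 | 0.1551 | 0.4649 |
| Paired, SD of difference 2.83 | 0.0867 | 0.2015 | 0.1016 | 0.2631 |
| Independent, SD 2 per finger | 0.09 | 0.22 | 0.11 | 0.28 |

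The range is therefore 0.09-0.35 at n = 12 and 0.10-0.46 at n = 16. At b = 0.25 the first row would be only 0.068 and 0.076.

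**4. Size of a haphazard choice**

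Suppose half the subjects are mismatched by d points in a random direction. With SD of the difference 2, the variance becomes 4 + 0.5d². For d = 0.5, 1 and 2 this is 4.125, 4.5 and 6, or 3%, 12.5% and 50% more subjects for the same precision. Modest random mismatch matters little.

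**The case against.** The strongest reply is that a package comparison is legitimate. The device description mentions the glove as a barrier, so the device as used may be meant to include it, and comparing that with an ordinary prick is sensible in a small study. This stands, and it is why the remedy is wording and not a new arm. It does not dispose of the point: the device description does not mention the blood-harvesting role, and Section 1 does not define the device to include the glove.

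A reader might infer more than the documents support:

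- *That the glove is known to reduce pain.* It is not. The description credits analgesia to cold and occlusive pressure from the ring; the glove's stated purposes are barrier and blood harvesting. A share in pain relief is inferred from its being a further constriction on the same digit.
- *That Aim 2 over-claims or the planned analysis is wrong.* Aim 2 credits nothing to the device, and no test of blood amount is planned. The over-attribution lies in the Section 1 hypothesis.
- *That digit and gauge will in fact differ within a subject.* The wording can mean both fifth or both third, and the two gauges may be supply alternatives. What is missing is a stated rule.
- *That a gauge imbalance could never be checked.* Section 6.b does not list gauge and Section 12.a names only pain scores for the case report form, but the Section 6.b list is not exhaustive (it omits blood pressure and adverse events). No recording of gauge is stated; that is all. Hand and digit should be recoverable from the images and video.
- *That 0.35 or 0.46 is the expected false-positive rate.* Those are the top of an assumed range, under a paired test with SD of the difference 2. The independent test named in Section 9 gives 0.09-0.22 and 0.11-0.28. Nothing in the documents shows that staff would choose in one direction.

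The randomisation sentence has a second reading: if the steps run as listed, control then chiller, it would assign the hand but leave order fixed. One of the two would still have no rule.

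**Conclusion.** The point holds in two parts. First, a difference in blood can be credited only to the package of rolled glove, glycerol, clamp and cooling. This follows from the procedure as written and rests on no numerical assumption. Extending it to pain is a reasonable inference, of unknown size.

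Second, the choice of chilled hand and the within-subject match of digit and gauge are left without a rule, which leaves an avoidable route to bias in the pain contrast. Its size is unknown; the 0.09-0.35 (n = 12) and 0.10-0.46 (n = 16) figures depend on an assumed systematic shift of 0.5 to 1 point. Digit and gauge are the lesser part. The study can still run, but the changes should be made because they are cheap and remove bias at its source.

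**What to change.** 1. In Section 1, and in the eventual conclusions, attribute any blood or pain difference to the package (cooling device with clamp, rolled glove and glycerol) against an ordinary finger prick. Reconcile Aim 1's venipuncture comparator with the control finger prick actually performed. A gloved control digit would separate out the glove, but the control would then no longer be an ordinary prick, so rewording is preferable here.
2. In Section 6.a (Visit 1), randomise which hand is chilled as well as prick order, balanced over the four hand-by-order cells: 12/4 = 3 per cell, or 16/4 = 4, once Sections 3 and 9 agree on the number of subjects.
3. Require the same digit and the same lancet gauge for both pricks within a subject, and record hand, digit and gauge on the case report form.
4. Reconcile Section 4.a and the device description (fifth finger only) with Visit 1 (fifth or third).

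Cost: a short amendment, a short randomisation list and three form fields, with no added procedure for subjects. The downside is a narrower claim and slightly less staff discretion.

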### ***First Follow-up Photo (6-8 days after Visit 1)***

Subject will be asked to send a photo of his treated fingers to MGH security email. The photos must be taken from the fingers and areas where the device has been applied. The photos will be sent by encrypted MGH email.

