### ***Second Follow-up Photo (27-31 days after Visit 1)***

Subject will be asked to send a photo of his treated fingers to MGH security email. The photos must be taken from the fingers and areas where the device has been applied. The photos will be sent by encrypted MGH email.

An optional visit can be requested by the investigator if he cannot evaluate the treated area by the photos or if he believes in person visit is needed for better clinical assessment.

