#### **b. Data to be collected and when data is collected**

Study data will be collected during screening and study visit. Study data to be collected includes Subject's reported pain scores with Wong-Baker pain rating scale, subjects' oximeter readings, subjects' video recording, subjects' photographs, and photographs of the Whatman 903 filter papers containing subjects' blood drops.

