**b. Device complications/malfunctions**

The device is designed to apply pressure to the two main feeder vessels to the digit. The pressure applied is controlled by the study physician who will monitor tissue blanching based on their clinical experience to ensure an appropriate amount of pressure/occlusion. In addition to monitoring pressure through tissue blanching, this study will limit the amount of time the device can be applied to the digit to 5 minutes. This time limit will be sufficient to prevent tissue ischemia, especially with the tissue cooling that will also be applied.

The device is designed to circulate propylene glycol cooling fluid at -2.5 degrees C. There are temperature indicators on the inlet and outlet tubing to the finger chiller. Temperature indicators will be checked and confirmed to be at the correct operating temperature prior to applying the device to subjects and during the finger pricking procedure.

If there were a leak of cold propylene glycol onto a subject's or study staff's skin, the temperature of the cooling fluid is not cold enough to cause significant damage. The propylene glycol portion of the cooling fluid in the system is a food-grade propylene glycol conforming to United States Pharmacopeia standards and is GRAS. According to the safety data sheet, it is considered to have low toxicity and may cause mild skin irritation. If the system is found to be leaking cooling fluid during the study, study staff will immediately remove the device from the subject and wipe the leaked fluid from the subject's or staff's skin. Study staff will clean the affected area in accordance with standard cleaning procedures for intact skin.

The circulating fluid is chilled and pumped by a commercially available liquid chiller. If the chiller fails to maintain the circulating fluid temperature or if the pump stops pumping fluid, the temperature of the finger cooling device may rise, the device may not provide sufficient analgesia to the tissue and the subject may feel pain. If the chiller fails to maintain the -2.5 temperature or the pump fails to circulate the fluid, the inlet and outlet temperature sensors near the clamp will rise, providing feedback to the

clinician to stop the experiment. Subjects will be instructed by study staff to immediately report any pain to the study physician performing the treatment. The subject has the right to stop the study at any time if they feel pain or otherwise wish to stop the study.

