### **d. Adverse Event Reporting**

#### *Definition*

Adverse Event (AE) is any untoward medical occurrence in a subject that does not necessarily have a causal relationship with this treatment. An AE can therefore be any unfavorable and unintended sign, symptom, or disease temporally associated with the use of an investigational product, whether or not related to the investigational product.

Serious Adverse Event (SAE) is any untoward medical occurrence that:

- Results in death
- Is life-threatening
- Requires inpatient hospitalization or prolongation of existing hospitalization
- Results in persistent or significant disability or incapacity
- Is a congenital anomaly/birth defect
- Is another medically important condition

*Reporting and Documenting Adverse Events*

All untoward medical occurrences that occur after the subject signs a consent form will be documented as an AE. The Investigator will ensure that all events that occur during the study period are recorded. All AEs will be followed until resolution or until, in the Investigator's judgment, they are chronic and stable. If an emergency situation should occur, appropriate medical measures should be taken to stabilize the subject.

Documentation of AEs includes date and time of onset and resolution of AE, intensity, frequency, seriousness, related interventions, and outcome. The Investigator will also evaluate the probability of a causal relationship of the AE to the study treatment as being: "definite, probable, possible, unlikely, or unrelated." Intensity of adverse events will be graded as mild, moderate, or severe according to the following criteria:

- Mild: symptoms that are easily tolerated and transient in nature with minimal or no impairment of normal activity
- Moderate: symptoms that are poorly tolerated, are sustained, and interfere with normal activity
- Severe: symptoms that are incapacitating and render the subject unable to work or participate in many or all usual activities

All SAEs will be reported to the IRB according to the IRB's requirements.

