## **12. Data Management**

### **a. Data collection**

All study data will be collected during study visits. Pain scores will be recorded on the case report form for visit 1. All physical documentation and IRB correspondence will be stored in study binders maintained in restricted lab space only accessible by study staff and members of the [name] Lab.

Digital data including photographs and video recording will be deidentified and stored on MGB computers. Any identifiable information in photographs tattoos will be blacked out and deidentified. Subjects' faces will not be recorded. All study documents containing PHI will be password encrypted, including the enrollment log and identification key. An encrypted external hard drive will be used to store the data as a backup.

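### Follow-up after nerve cooling relies on subject-sent photos, and no scheduled contact is specified to ask about numbness, tingling or cold sensitivity

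*Combined protocol and SAP*

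**What the plan says.** The device description in section 6 states the mechanism: the applicator cools the nerves to a temperature below which "nerve conduction from the distal portion of the digit reduces and/or ceases".

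For Visit 1, section 6.a lists blood pressure, oximetry, thermal imaging, a pain score for each prick, blood collection on filter paper, images, video and removal of the device. On safety it says: "Study staff will document any anticipated side effects or Adverse Events that occur during the study visit". No test or question on the return of feeling is listed.

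After Visit 1 there are two scheduled contacts, at days 6-8 and 27-31, both worded alike: "Subject will be asked to send a photo of his treated fingers to MGH security email". The investigator may also request an in-person visit "if he cannot evaluate the treated area by the photos or if he believes in person visit is needed for better clinical assessment".

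Sections 10.b and 10.d add general duties: evaluation for adverse events continues through the study, every untoward event after consent is recorded, and each is followed until it resolves or is stable. The required content is specific: "Documentation of AEs includes date and time of onset and resolution of AE, intensity, frequency, seriousness, related interventions, and outcome".

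The one explicit instruction to subjects about reporting a symptom is in section 7.b and concerns the procedure itself: "Subjects will be instructed by study staff to immediately report any pain to the study physician performing the treatment".

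**The concern.** The intended effect of the device is loss of feeling, so the unwanted effect most directly linked to it is feeling that returns late or incompletely. The subject can notice this but a camera cannot record it. The scheduled follow-up method therefore suits skin injury and does not suit the mechanism under test.

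This matters because section 1 hypothesises that the device works safely as well as effectively, and the device description asserts that application for up to 10 minutes carries no risk. If the study later reports that no lasting effects were seen, a reader will want to know whether anyone asked. For sensory symptoms, the protocol as written cannot answer that. A subject with a mildly tingling finger and a normal-looking photo may say nothing, and the investigator would then have no cue to use the optional visit.

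**Working it through.** The plan gives no figure on this point, so there is none to reproduce. The check sets what is scheduled beside what it can show.

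| Time | Specified in the protocol | Can it show numbness, tingling or cold sensitivity? |
|---|---|---|
| Visit 1 (6.a) | Pain score per prick; oximetry; temperature; images and video; adverse events documented by staff | Only if the subject mentions it or staff ask; no check of returned sensation is listed |
| Days 6-8 (6.a) | Photo sent by the subject | No |
| Days 27-31 (6.a) | Photo sent by the subject | No |
| Optional visit (6.a) | At the investigator's request | Yes, but a clear photo of a numb finger need not prompt it |
| Throughout (10.b, 10.d) | Adverse events detected, recorded and followed | Yes if volunteered; no method of asking after Visit 1 is given |

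**Timing.** The first scheduled contact comes 6 to 8 days after the procedure. The interval to the second runs from 27 − 8 = 19 days to 31 − 6 = 25 days. Neither contact has a specified symptom question.

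**Named risks.** Section 7.a lists pain, swelling, edema, redness and bruising from the prick. Section 7.b covers occlusion, coolant leakage and loss of cooling. Neither names lingering numbness, tingling or cold sensitivity, so the risk section does not prompt staff to look for them.

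**Size.** The amount of under-recording would depend on the true rate of sensory symptoms and the share that subjects report without being asked. The documents give neither, so no figure can be derived. With 12 subjects and no recorded event, the exact one-sided 95% upper limit is 1 − 0.05^(1/12) = 0.221, or 22.1%. That limit assumes every event is captured. It reflects the sample size and stays the same whether or not questions are added. Questions would make the complete-capture assumption more credible, but 22.1% does not measure this gap.

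**Burden of asking.** 5 questions × 2 digits × 2 contacts = 20 yes/no answers per subject.

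**The case against.** The strongest reply is that routes to capture already exist. Section 10.d makes the investigator responsible for recording all events in the study period, not only those at Visit 1. Section 10.b calls for continuing evaluation. The optional visit is open whenever the investigator thinks it clinically useful. Numbness is the intended effect, so residual numbness could be read as an anticipated side effect that staff document at Visit 1. Subjects are healthy adults fluent in English who are already corresponding with the site, and a persistently numb finger is something they may well mention. All of this stands, and it reduces the point to the lack of a written prompt.

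Expected risk is also low. Contact is limited to 5 minutes in section 7.b, or 7 minutes in the device description. Tissue is cooled to 0-7.5°C, and people with cold sensitivity or cold-induced disease are excluded. Neither aim in section 2 is a safety aim, the primary outcome in section 9 is pain, and no safety analysis is planned. This too stands, and it is why the point is a cheap improvement and not a flaw in the main comparison.

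The case report form, the photo-request email and the consent pages are not available here, and any of them might already contain a symptom question. The point is therefore confined to what the protocol specifies.

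A reader might take the data sections as proof that symptoms are not collected. Section 6.b says "Study data will be collected during screening and study visit" and section 12.a says "All study data will be collected during study visits". These cannot bear that weight: read literally, both would also exclude the follow-up photos. The list in 6.b omits blood pressure and adverse events too, so it is not exhaustive.

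Nor should the content required for an adverse-event record be held against the photos. Those details are due once an event is known, and nothing suggests a photo was meant to supply them.

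**Conclusion.** The point holds as a gap in active solicitation. The protocol tests a device that acts on sensation, specifies no check that sensation has returned at Visit 1, and schedules only photos afterwards. Sensory symptoms may therefore be under-recorded.

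Three stronger conclusions might be inferred, and the documents support none of them. The first is that sensory events would go unrecorded: they would be captured if volunteered. The second is that the device is likely to harm subjects: nothing in the documents indicates this. The third is that the under-recording can be given a number, for example by dividing the 22.1% limit by an assumed capture share: any such share would be invented.

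The judgement rests on two assumptions: that no unseen study document already asks these questions, and that some subjects would not mention a mild symptom unprompted. If the case report form or email already asks, the sponsor need only say so in sections 6.a and 6.b.

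**What to change.** Attach one short fixed set of yes/no questions to each photo request at days 6-8 and 27-31: numbness, tingling, pain, cold sensitivity and colour change. Ask the same questions about **both** the chilled and the control digit. Both are lanced, so pain or colour change in the chilled digit alone cannot be attributed to the device without the other digit for comparison. A difference between digits would reflect the whole chilled-digit procedure, including the rolled glove and the clamp pressure, and not cold alone. Assess positive answers as adverse events under section 10.d, and let them prompt consideration of the optional visit.

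At the end of Visit 1, add one case report form line recording whether sensation in the chilled digit matches the control digit. Treat short-lived numbness as expected. The documents give no recovery time, so the investigator should state beforehand what counts as short-lived.

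The cost is 20 answers per subject within two requests already being sent, one form line, possibly a few more minor adverse events, and IRB approval of the amendment and questionnaire under section 13. No aim, sample size or planned analysis changes.
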